## **Research Question and Aims**

#### **Hypothesis**

This study will adapt intervention components that were previously validated in several pragmatic clinical trials: E2C2 (#18-007779), NOHARM (#20-004839) and COPE (#11-008151), for remote delivery to rural dwelling and Hispanic Cancer Survivors. We will refine the sociocultural, linguistic, IT, and clinical aspects of the intervention through iterative design cycles. We recognize that the needs of the targeted subgroups are heterogeneous and may require patient-specific matching of language, IT modes, extent of portal-based delivery, among other aspects, in order to optimize patient engagement and experience. Intervention components will be integrated and tested in a future parallel group, two-arm randomized clinical trial at six Mayo Clinic sites. The full trial is anticipated to begin later this year under a separate IRB application.

We hypothesize that an iteratively refined, EHR-based modular approach that combines specific intervention components in accordance with a patient's sociocultural, IT, and linguistic needs, will demonstrate fidelity, usability, and acceptability among our target population of Hispanic, rural dwelling, and rural dwelling Hispanic cancer survivors experiences moderate or worse pain.

#### Aims, purpose, or objectives

To refine and pilot test components of a validated collaborative care model-based intervention aimed at improving pain control among rural dwelling and Hispanic cancer survivors. The intervention will align pain care with evidence-based best practices and address SDOH and other barriers to patients' receipt of appropriate care. The pilot will emphasize sociocultural, linguistic, and IT adaptation of the intervention for the target demographic to inform the implementation of the future Achieving Equity through SocioCulturally-informed, Digitally Enabled Cancer Pain ManagemeNT (ASCENT) randomized control trial.

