## **Study Design and Methods**

#### Methods

In this pilot, we will test our ASCENT intervention at the following Mayo Clinic locations: Rochester, Arizona, Florida, Mankato, Eau Claire and La Crosse. For this minimal risk study without in-person patient contact, patients can be recruited from the previously mentioned locations, but research activities are only being conducted at Mayo Clinic Rochester and Mayo Clinic Arizona. We will recruit three groups of individuals: Rural, Hispanic, Rural & Hispanic. Participants who are experiencing cancer-related pain and who meet inclusion criteria will be recruited and will have the opportunity receive additional education material in an initial mailing as well as support from Pain Care Managers (PCMs) and Community Health Workers (CHWs) to manage their pain. The study team will provide as much material as possible in Spanish for participants who speak only Spanish or prefer to read in Spanish. The study team includes members who speak Spanish fluently. These members may include, but are not limited to study coordinators, PCMs, CHWs, and other support staff. If a patient speaks only Spanish and the team member does not, a telephone interpreter will be utilized. PCMs and CHWs will follow a validated pain management algorithm that includes evidence based and guideline-endorsed best practices for managing cancer related pain and addressing Social Determinants of Health (SDOH) barriers to receipt of recommended care. The ASCENT interventions in this pilot protocol and the future randomized trial align with the NCCN guideline for the management of cancer-related pain.

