## **Part 1 – Testing the ASCENT Intervention Components**

#### Intervention

Potentially eligible participants will be identified using data found in the Epic EHR Chronicles database, including qualifying appointments, ethnicity, RUCA highly rural zip code, and cancer diagnoses (Approved in IRB# 22-008103). Patients who meet the electronic criteria listed in this protocol will receive information about our study and a pain Numeric Rating Scale (NRS) questionnaire via the patient portal, Welcome tablet functionality, or Interactive Voice Response (IVR). We are seeking a waiver of consent due to the volume of patients this would involve across the 6 participating sites, and the fact that symptom monitoring is considered a best practice in caring for cancer survivors. IVR is an automated telephone service provided by an external vendor (RevSpring). Research coordinators will attempt to enroll and formally consent patients who endorse

pain  $\geq$ 5/10 and who respond to this initial outreach. Recruitment calls will also be made to screen patients who do not respond for pilot eligibility (See Recruitment & Consent section for more details). Patients will be able to opt out of hearing more information or being contacted by a study coordinator at multiple points in the trial recruitment and enrollment procedures. After consent, participants may be sent additional education materials in an initial mailing. The engagement, intake, visit 2, final visit, and follow up calls will be recorded for fidelity monitoring. All study visits will be conducted via telephone or video call.

We will test prototype recruitment scripts in English and Spanish. At the end of the recruitment process, participants will be queried about their experience. For each call, CRCs will indicate sections of the script that seemed wordy, awkward, confusing, or prompted questions from prospecive participants. We will additionally record recruitment conversations. Tapes will be reviewed by Hispanic and rural dwelling citizen scientist ASCENT team members, ASCENT implementation scientists, and CRCs.

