#### **Subject Information**

Target accrual is the proposed total number of subjects to be included in this study at Mayo Clinic. A "Subject" may include medical records, images, or specimens generated at Mayo Clinic and/or received from external sources.

Target accrual: 140 (maximum). Accrual will depend on the nature and extent of sociocultural and linguistic tailoring, and the number of iterative design cycles. This total includes 40 participants for the pilot study itself, up to 40 participant interviews, up to 15 study team interviews and up to 45 providers for focus groups.

Subject population (children, adults, groups): Adults

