#### *Oualitative data*

We will incrementally and iteratively develop a coding scheme beginning with the first transcript. Categories, groups of content sharing common features, will be created and abstraction of the text will be accomplished by assigning category codes. Subcategories will be identified to further delineate the content. Finally, themes or ideas that cut across categories will be created. As new concepts emerge, they will be defined and added to the coding scheme. If data saturation is not reached we will consider the need for additional interviews.

Future trial endpoints

Primary: Brief Pain Inventory

Secondary: PROMIS Physical Function, Sleep Disturbance and Anxiety Computerized Adaptive Tests We will assess the psychometric performance of the PROM study endpoints in target subgroups. In addition to calculating descriptive statistics for primary and secondary outcomes at baseline and when participants go off study, we will graph PROM scores in aggregate and by demographically-defined subgroups to assess for ceiling and floor effects and distribution of scores across the full trait range. Although the anticipated sample sizes will be limited, 20 Hispanics and 20 rural dwellers, we will compare measures of central tendency and variance in participants' PROM scores to those reported for other cohorts and used to calculate the full trial's sample size. This will clarify the whether review of the trial's power calculation is warranted.

Effective: 9/20/2017

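### Linguistic adaptation is one of the pilot's three stated emphases, but no planned count, breakdown or stopping criterion requires evidence from people who used the Spanish versions

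*Combined protocol and SAP*

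**What the plan says.** Under Aims, purpose, or objectives, the protocol says: "The pilot will emphasize sociocultural, linguistic, and IT adaptation of the intervention for the target demographic". The Hypothesis and Background sections also name linguistic fit as something to be refined.

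Provision for Spanish speakers is real. Methods says: "The study team will provide as much material as possible in Spanish for participants who speak only Spanish or prefer to read in Spanish". It adds Spanish-speaking staff and telephone interpreters. Part 1, Intervention, says: "We will test prototype recruitment scripts in English and Spanish".

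The sample is described in other terms. Methods says: "We will recruit three groups of individuals: Rural, Hispanic, Rural & Hispanic". Patients are found from EHR data "including qualifying appointments, ethnicity, RUCA highly rural zip code, and cancer diagnoses". Subject Information gives the size: "This total includes 40 participants for the pilot study itself". The text on future trial endpoints divides it: "Although the anticipated sample sizes will be limited, 20 Hispanics and 20 rural dwellers".

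For reporting, PROM scores are to be plotted overall and "by demographically-defined subgroups to assess for ceiling and floor effects". PROM collection breaks response rates down in similar terms. Neither place defines these subgroups.

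Two criteria govern iteration. Under Optimized components and process, refinement of a component ends once 80% of the Delphi participants agree on four attributes: sociocultural appropriateness, usability, patient-centricity and acceptability. Under Response rates, the goal is above 90% for PROMs, recruitment questionnaires and remote pain assessments, with no figure by language.

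**The concern.** Ethnicity does not determine language of delivery. A Hispanic participant may complete everything in English, so a result for Hispanic participants describes an unknown mixture of English and Spanish delivery. If the Spanish versions work less well, whether in response, engagement or PROM score distribution, the pooled figure can conceal it.

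The Delphi criterion has a second consequence. Once agreement is reached, refinement of that component stops. Nothing requires the panel to have seen a Spanish version in use, so that version could enter the randomised trial without having been tried.

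**Working it through.** **1. The plan's own counts.** Subject Information: 40 + 40 + 15 + 45 = 140, as stated. Pilot participants: 20 Hispanic + 20 rural = 40, as stated. No count by language is given.

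**2. Where language could enter, step by step.**
- Identification: appointments, ethnicity, rural zip code and cancer diagnosis. Language is not listed.
- Recruitment groups and planned numbers: ethnicity and rurality.
- Questions listed for the recruitment call: access to devices and broadband, IT fluency, preferred mode for PROMs. Preferred language is not listed.
- Touchpoint measures under Measurement: none is specified by language.
- Subgroups for response rates and PROM plots: demographic, undefined.
- Delphi criterion: four attributes, with no condition on use of the Spanish version.
- Response goal: not set by language.

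**3. Can the response goal be met despite failure in Spanish?** Take the 40 pilot participants as denominator. 36/40 is exactly 90% and does not exceed it; 37/40 = 92.5% does. So 40 − 37 = 3 non-responders are allowed. Three Spanish-preferring participants could all fail to respond and the goal would still be met. Among 20 Hispanic participants, 18/20 = 90% falls short and 19/20 = 95% passes, so one non-responder is allowed.

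**4. How many Spanish-preferring participants might there be?** The share p is not in the documents, so it is an assumption, shown here from 10% to 50%. With X ~ Binomial(20, p):

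P(X < 5) = Σ (k = 0 to 4) C(20, k) p^k (1 − p)^(20 − k)

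At p = 0.2 the terms are 0.012 + 0.058 + 0.137 + 0.205 + 0.218 = 0.630.

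| Assumed share | Expected number | P(2 or fewer) | P(fewer than 5) |
|---|---|---|---|
| 10% | 2 | 68% | 96% |
| 20% | 4 | 21% | 63% |
| 30% | 6 | 3.5% | 24% |
| 40% | 8 | 0.4% | 5% |
| 50% | 10 | <0.1% | 0.6% |

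This takes 20 as the whole Hispanic sample. The documents do not say how the Rural & Hispanic group is counted. If some of the 20 rural dwellers are also Hispanic, the Hispanic total is larger and these chances are lower.

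**5. What a few Spanish users can show.** If all n respond, the exact two-sided 95% lower limit for the response rate is 0.025^(1/n): 16% for n = 2, 29% for n = 3, 48% for n = 5 and 69% for n = 10. Even complete response from a handful says little about a 90% goal.

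**The case against.** The strongest reply is that the plan already attends to Spanish. Scripts are tested in both languages. Coordinators flag problem sections on every call, and recordings are reviewed by Hispanic and rural citizen scientists. Up to 40 interviews run toward thematic saturation, and Subject Information makes accrual depend partly on how much linguistic tailoring is needed. All of this stands as mitigation. None of it sets a number of Spanish users, a breakdown by language, or a condition on the Delphi criterion.

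Several stronger readings are tempting and should not be adopted:
- *Language is the pilot's sole emphasis.* It is one of three.
- *The analysis excludes language.* The subgroups are undefined. Language could be meant, but nothing says so.
- *The Spanish group will be nearly empty.* That is likely at a share of 10%, unlikely at 30% and very unlikely at 40% or more. The documents do not say which applies.
- *A problem affecting one in five Spanish users would go unseen with probability 0.8^n.* Scripts are tested on all recruitment calls, including calls to people who do not enrol, and reviewers can spot faults that no user reports. The formula applied to enrolled participants does not describe that process.
- *The plan will certify Spanish PROM administration as ready.* It makes no such declaration. PROMs are collected to assess completeness and fidelity of collection, and score comparisons only show whether the trial's power calculation needs review.

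**Conclusion.** The point holds as a gap in what the pilot can conclude, not as a forecast that Spanish testing will fail. It rests on the text: neither the Delphi criterion nor the response goal depends on Spanish use. That is true whatever the Spanish-preferring share.

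The share affects only how thin the evidence may be. If it is 20% or less, fewer than 5 Spanish-preferring participants is the more likely outcome; at 40% or more, that outcome is improbable. Even with a well-filled Spanish group, results pooled by ethnicity would not separate Spanish from English delivery. The change is worth making because it bears directly on a stated aim and costs almost nothing.

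**What to change.** Three changes to the text:

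1. At the recruitment call, record preferred language as a data item. Staff need to know it anyway in order to deliver materials.
2. Under PROM collection and Future trial endpoints, state that the subgroups include language of delivery. Report counts, response rates, engagement ratings, participant feedback and PROM distributions for English and Spanish delivery, alongside ethnicity and rurality.
3. Under Optimized components and process, add: a Spanish-language component is counted as optimized only if the Delphi panel has reviewed data from participants or calls that used the Spanish version; otherwise it is reported as untested.

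The cost is one extra field and one extra breakdown, with no added participants. Cells by language will be small and should be presented descriptively. Some Spanish components may end the pilot reported as not yet optimized, which is the information the later trial needs. Reserving places for Spanish-preferring patients is not required: any number would be arbitrary, and a quota would add screening work because patients are identified by ethnicity and contacted at most three times.

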## **Background**

Cancer pain is a key case study in health disparities in the US. Cancer pain is prevalent, undertreated, and remains a major cause of suffering, impairment, and disability for millions of Americans. Individual pain interventions and care models show promise for cancer pain in controlled settings. Unfortunately, typical approaches too often target limited aspects of the whole, fail to consider health disparities populations (HDPs), and are unable to serve broad and diverse populations. This situation will only worsen with time. For example, by 2030, the number already underserved Hispanic cancer survivors in the U.S. will increase to 4 million.

Hispanic and rural-dwelling cancer survivors stand to benefit the most from EHR innovations, as each of these HDPs experience profound disparities in pain outcomes, including marked under- and over-prescribing of opioids. Additionally, Hispanics not only comprise a steadily growing proportion of cancer survivors, but are also increasingly immigrating to rural communities, potentially placing them at "double risk" for poor outcomes. Digitally-facilitated solutions are especially well matched for these disparities, and can be customized to address the overlapping, yet distinct, needs of these HDPs. Doing so would provide a vital proof of concept and may illustrate the promise of digitally based, patient-centered approaches to mitigating other disparities.

This preparatory pilot study will allow iterative refinement of intervention components and study procedures to optimize their sociocultural and linguistic appropriateness, feasibility, and acceptability. The study will optimize patient-facing cancer pain support components of an EHR-facilitated, evidence-based bundle in a manner that meets the diverse needs of the target sample.

## **Study Design and Methods**

#### Methods

In this pilot, we will test our ASCENT intervention at the following Mayo Clinic locations: Rochester, Arizona, Florida, Mankato, Eau Claire and La Crosse. For this minimal risk study without in-person patient contact, patients can be recruited from the previously mentioned locations, but research activities are only being conducted at Mayo Clinic Rochester and Mayo Clinic Arizona. We will recruit three groups of individuals: Rural, Hispanic, Rural & Hispanic. Participants who are experiencing cancer-related pain and who meet inclusion criteria will be recruited and will have the opportunity receive additional education material in an initial mailing as well as support from Pain Care Managers (PCMs) and Community Health Workers (CHWs) to manage their pain. The study team will provide as much material as possible in Spanish for participants who speak only Spanish or prefer to read in Spanish. The study team includes members who speak Spanish fluently. These members may include, but are not limited to study coordinators, PCMs, CHWs, and other support staff. If a patient speaks only Spanish and the team member does not, a telephone interpreter will be utilized. PCMs and CHWs will follow a validated pain management algorithm that includes evidence based and guideline-endorsed best practices for managing cancer related pain and addressing Social Determinants of Health (SDOH) barriers to receipt of recommended care. The ASCENT interventions in this pilot protocol and the future randomized trial align with the NCCN guideline for the management of cancer-related pain.

## **Part 1 – Testing the ASCENT Intervention Components**

#### Intervention

Potentially eligible participants will be identified using data found in the Epic EHR Chronicles database, including qualifying appointments, ethnicity, RUCA highly rural zip code, and cancer diagnoses (Approved in IRB# 22-008103). Patients who meet the electronic criteria listed in this protocol will receive information about our study and a pain Numeric Rating Scale (NRS) questionnaire via the patient portal, Welcome tablet functionality, or Interactive Voice Response (IVR). We are seeking a waiver of consent due to the volume of patients this would involve across the 6 participating sites, and the fact that symptom monitoring is considered a best practice in caring for cancer survivors. IVR is an automated telephone service provided by an external vendor (RevSpring). Research coordinators will attempt to enroll and formally consent patients who endorse

pain  $\geq$ 5/10 and who respond to this initial outreach. Recruitment calls will also be made to screen patients who do not respond for pilot eligibility (See Recruitment & Consent section for more details). Patients will be able to opt out of hearing more information or being contacted by a study coordinator at multiple points in the trial recruitment and enrollment procedures. After consent, participants may be sent additional education materials in an initial mailing. The engagement, intake, visit 2, final visit, and follow up calls will be recorded for fidelity monitoring. All study visits will be conducted via telephone or video call.

We will test prototype recruitment scripts in English and Spanish. At the end of the recruitment process, participants will be queried about their experience. For each call, CRCs will indicate sections of the script that seemed wordy, awkward, confusing, or prompted questions from prospecive participants. We will additionally record recruitment conversations. Tapes will be reviewed by Hispanic and rural dwelling citizen scientist ASCENT team members, ASCENT implementation scientists, and CRCs.

All data used to direct the IVR calls is maintained on Mayo Clinic servers and no data are released to RevSpring. RevSpring has been used by the Mayo Clinic Spine Center to securely administer follow-up patient reported outcome measures to over two thousand patients. The ASCENT pain NRS questionnaire responses will reside on our server and will not go outside of the firewall. Data going to the RevSpring platform is transient in nature and is purged once the results are uploaded into Epic. TAP approval has been granted to RevSpring's IVR system and there are Business Associate Agreements (BAA) and Information Security Agreements (ISA) in place, which covers how PHI can be used and stored.

Recruitment Call: The research coordinator will formally recruit interested and eligible participants. Eligibility criteria include a pathologically confirmed solid or liquid cancer diagnosis, excluding acute leukemia, within 15 years of study enrollment; pain rated  $\geq 5/10$ ; and a PH8-8 score of  $\leq 9$ . The pilot study will be described to eligible patients. Patients who consent ot participate will be asked questions to determine their access to and facility with technological devices, and the extent to which they can access broadband internet. Should the participant need a device to participate in the visits described in this protocol, the study team will send one to them for temporary use. The research coordinator will then schedule a time for the participant to meet with the Pain Care Manager (PCM) and Community Health Worker (CHW) either via telephone or video visit.

Engagement Call: The CHW will meet with the participant via video visit or telephone to discuss the ASCENT study, gain an initial understanding of the patient's pain, and introduce the practice of keeping a pain journal. The CHW will also obtain patients' SDOH background to identify barriers that may impact their ability to access pain treatment. The CHW will review first and second-line treatment options so that the patient is aware of the treatment options available to them. This conversation will be informed by a "Conversation Guide" bundle developed for the study.

Intake Visit: The PCM and CHW will meet with the participant via video visit or telephone to discuss the cancer-related pain they are experiencing (PCM), as well as obtain their SDOH background to help identify barriers that may impact their ability to access pain treatment (CHW). The PCM and CHW will work with the patient to develop an action plan to help address their pain by utilizing a "Conversation Guide" bundle developed for the study. This guide will share approved patient education materials for self-guided pain management, provide information on online tools, (such as our study website) and structure interaction between the participant and PCM/CHW. Participants will be able to receive the

Conversation Guide in a variety of formats per their preference (portal, paper mailing, web, email, etc). The conversation between the PCM and the participant will lead the PCM to make suggestions/referrals from the below Tier 1 and Tier 2 interventions, which consist of 6 treatment domains.

Tier 1
Exercise
Cognitive Behavior Therapy (CBT)
Medicine

Tier 2
Integrative Medicine
-Massage
-Acupuncture
-Mindfulness
Spiritual Support
Pain Clinic Referrals
Palliative and Spiritual Care Referrals

Planning Visit: A second visit will take place approximately 2 weeks after the intake visit, depending on the availability of the participant, PCM and CHW. In this visit, the participant will give an update on their pain and additional resources may be suggested by the PCM and/or CHW.

Final Visit: The third visit will be the final visit between the participant, PCM and CHW and will take place approximately 4 weeks after the intake (depending on patient, PCM and CHW availability). Participant progress will be reviewed, final recommendations and referrals will be made.

Participant Surveys: After a participant has completed the three visits listed above, they will be sent a short survey via email, mail or portal to give feedback about their experience. Telephone may also be used to administer the survey. This feedback may help facilitate any necessary changes for the future ASCENT trial.

Follow Up Visits & NRS pain surveys: the CHW or PCM may conduct follow up calls between intake and visit 2 and/or between visit 2 and the final visit. As pain levels, SDOH barriers and level of needed assistance vary from patient to patient, these will be scheduled as needed on a participant-by-participant basis at the discretion of the PCM/CHW and participant. Additionally, the participant will receive regular pain NRS surveys via portal and/or IVR. CHWs and PCMs will check in with patients via portal or text message to see how patients are doing and if follow up visits are required.

**Remuneration**: Participants will be reimbursed for their participation in this study. They will receive \$50 for the intake visit, \$50 for visit 2, \$50 for the final visit and \$20 for the completion of the participant survey for a total of up to \$170. No remuneration will be given for recruitment or follow up calls. Payment will be submitted within 2 weeks of study completion after which Mayo Accounting will process a check or direct deposit via payroll for Mayo Employees.

Care Manager Conferences: The ASCENT study team will work collaboratively with Medical Oncology, Social Work, Physical Therapy, Palliative Care, and other applicable areas to address patient needs. Care Manager Conferences will take place weekly during this pilot to ensure that participant situations require a collaborative approach can be addressed in a timely manner. During the conferences the PCM will present the patient's pain and related issues to an interdisciplinary group of pain specialists potentially including

Rehabilitation Medicine, Hospice and Palliative Medicine, Pain Medicine, and Pain Psychology. This is a best practice approach that is integral to clinical practices across the Mayo Clinic Enterprise. Participants will not be involved in these conferences but the feedback gathered will help the PCM/CHW assist the participant.

